1.1 Primary objectives

- 1.1.1 To determine treatment efficacy defined as histologic regression to CIN 1 or less at weeks 20-24 (4 to 8 weeks after the end of imiquimod treatment) in the HPV Vaccine + Imiquimod group compared to control
- 1.1.2 To determine treatment efficacy defined as histologic regression to CIN 1 or less at weeks 20-24 (4 to 8 weeks after the end of imiquimod treatment) in the Imiquimod group compared to control

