5.0 CORRELATIVE STUDIES

5.1 Histopathology: Cervical biopsies will be collected at the time of initial colposcopic evaluation based on clinical guidelines for management of abnormal pap tests. Cervical biopsies will be processed

HIC#: 1603017415 Protocol version 11.0

in the surgical pathology department. Cervical biopsies with high-grade (CIN 2/3) dysplasia will be centrally reviewed and diagnosis confirmed by study pathologists, in the Pathology Department at Yale University. Subjects with confirmed CIN 2/3 are eligible for enrollment. Colposcopy will be performed and cervical biopsies collected during weeks 20-24 (4-8 weeks after completion of Imiquimod therapy) will be centrally reviewed in the Pathology Department at Yale University to assess for the primary outcome. Pathologists will be blinded to study randomization.

5.2 HPV DNA Testing & HPV 16/18 Genotyping: Confirmatory high-risk HPV DNA testing will be performed under supervision of cytopathologist [name] in the Pathology Department at Yale University from cervical cytobrush sample obtained on day of enrollment. HPV 16/18 genotyping will be performed via PCR from cervical cytobrush sample by [name] Lab to establish baseline HPV status. This testing will be repeated between weeks 16-18 from cervical cytobrush samples and at final study visit during weeks 20-24 or following at least 3 weeks after completion of imiquimod therapy.

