arms), a review of medication diary, monitoring of correct use of study medication, and report of local and systemic side effects using a standardized case report form will occur at all follow up visits. For women who received HPV vaccine as part of study protocol (Imiquimod + HPV vaccine arm), a review of vaccination diary and report of local and systemic side effects using a standardized case report form will occur at all follow up visits. A pelvic exam will be performed to objectively assess for gross cervical lesions in all subjects and also for local side effects from imiquimod use in the Imiquimod only and Imiquimod + HPV vaccine arms. Endocervical cytobrush samples will be obtained at this time. HPV 16/18 genotyping will be performed using endocervical cytobrush samples at this time point. Colposcopy and cervical biopsies will be performed as clinically indicated. Blood sample collections will also occur.

Week 22 (20-24 weeks): This visit will be timed to occur at least 3 weeks after completion of imiquimod treatment course. For women using imiquimod (Imiquimod only and Imiquimod + HPV vaccine arms), a review of medication diary, monitoring of correct use of study medication, and report of local and systemic side effects using a standardized case report form will occur at all follow up visits. For women who received HPV vaccine as part of study protocol (Imiquimod + HPV vaccine arm), a review of vaccination diary and report of local and systemic side effects using a standardized case report form will occur at all follow up visits. A pelvic exam will be performed to objectively assess for gross cervical lesions in all subjects and also for local side effects from imiquimod use in the Imiquimod only and Imiquimod + HPV vaccine arms. Endocervical cytobrush samples will be obtained at this time. High risk HPV test and HPV 16/18 genotyping will be performed using endocervical cytobrush samples at this time point. Colposcopy and cervical biopsies will be performed on all subjects at this final study visit to assess primary endpoints. Blood sample collections will also occur.

Persistence of CIN 2-3 or worsening cervical dysplasia diagnosed at the 20-24 weeks visit will be recommended for treatment with surgical conization.

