7.3 Treatment compliance

The study medication will be given in accordance with the protocol and the instructions of the investigator.

The appropriate number of imiquimod suppositories for the first 8 weeks of imiquimod treatment course will be provided to subjects to be self-administered at home. At week 8 follow up visit, the appropriate number of imiquimod suppositories for weeks 9-16 imiquimod treatment course will be provided to subjects. Subjects will be asked to bring the remaining study medication at each follow-up visit (weeks 8, 16) to the investigator site for a compliance check. The remaining suppositories will be counted by the investigator/site staff and recorded at the investigator site. Discrepancies between the number of suppositories remaining and the calculated number the subjects should have used must be documented and explained. At the end of the 16-week period, any remaining medication will be collected.

The investigator can withdraw a subject from the study in the event of serious and persistent non-compliance which jeopardizes the subject's safety or render study results for this subject uninterpretable.

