10.0 EVALUATION CRITERIA

10.1 Objective Response

The major parameters of response to be assessed include treatment efficacy defined as histologic regression of cervical dysplasia to CIN 1 or less 12 to 16 weeks after the end of imiquimod treatment, HPV clearance and treatment tolerance.

- 10.11 Histologic regression: Only subjects with histologically confirmed CIN 2,3 as reviewed by a central study pathologist will be enrolled in the study. All index biopsy sites noted to have CIN 2,3 at baseline must be assessed via colposcopy. Cervical biopsy at the final colposcopy will be collected from the worst areas of residual disease. Included in the evaluations are the following criteria:
 - Histologic regression (HR): Histologic regression of all index lesions to CIN 1 or less at 12 to 16 weeks after end of imiquimod treatment period.
 - Histologic remission (HM): Complete regression of cervical dysplasia at all index biopsy sites at 12 to 16 weeks after end of imiquimod treatment period.
 - Persistent Disease (PR): One or more index lesions persists with CIN 2,3 high grade dysplasia or new lesions are identified colposcopically and histologically confirmed to be CIN 2,3.
 - Progressive Disease (PD): Worsening histology of an index lesion.
- 10.12 HPV Clearance: HPV clearance will be measured by both the Roche cobas HPV Test utilized by pathology concomitant with the pap test at final study visit which assesses for presence of 14 high risk HPV types as well as HPV 16/18 genotyping performed by [name] Lab.
- 10.13 Treatment Tolerance: The grade level of the various toxicities will be classified using the Common Toxicity Criteria, version 4 (CTC, v.4) guidelines. Acute toxicities will be scored if occurring </= 30 days from treatment completion, and chronic if > 30 days. Frequency and duration of treatment interruptions due to the treatment toxicity will be assessed.

11.0 **DURATION OF STUDY**

11.1 This study will continue as long as treatment protocols remain activated.

HIC#: 1603017415 Protocol version 11.0

CIN 2/3

11.2 The subject will be followed with routine clinical care with a 6 month colposcopy and cytology if histologic remission or regression noted at final study visit and in 12 months if cytology remains negative with normal colposcopy. Any abnormal cytology or colposcopy at 6 months should prompt cervical biopsy and management per guidelines of American Society for Colpsocpy and Cervical Pathology (ASCCP).

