15.5 Analysis for the Primary Objective

The co-primary objectives of this study are to test superior treatment efficacy of Imiquimod + HPV vaccine (Trt1) compared to control (Trt0), and likewise Imiquimod only (Trt2) compared to control (Trt0). The primary outcome is *histologic regression* (yes/no) after completion of the 12 to 16 weeks imiquimod course. The full definition of *histologic regression* and how it is determined is described in Section 5.1.

The co-primary hypothesis tests are:

 $\{H_{01}: p_1 - p_0 = 0 \text{ versus } H_{11}: p_1 - p_0 > 0\}$ and

 $\{H_{02}: p_2 - p_0 = 0 \text{ versus } H_{12}: p_2 - p_0 > 0\}$

 p_0 , p_1 , and p_2 are the proportion of subjects on Trt0, Trt1, and Trt2, respectively, who are determined to have *histologically regressed*. Fisher's Exact Test will be used to assess if the data support rejecting the null hypothesis H_{01} , and likewise for H_{02} . To control Type I error, we will use a conservative Bonferroni adjustment for multiple comparisons with one-sided $\alpha = (0.05)/2 = 0.025$ as the significance level for each test. Rejection of a particular null hypothesis suggests superior efficacy of that specific treatment compared to control. Exact 95% confidence intervals will be calculated for p_1 - p_0 and for p_2 - p_0 . Confidence intervals for 'risk ratios' (p_1/p_0 , p_2/p_0) in addition to 'risk differences' (p_1 - p_0 , p_2 - p_0) may also be estimated. The main analysis will use the **modified ITT analysis set**. Sensitivity analyses for the same statistical method using the **modified ITT completers** and/or **per protocol analysis sets** may also be provided.

HIC#: 1603017415 Protocol version 11.0

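### Sections 10.1 and 10.11 time histologic regression and remission at weeks 28-32, outside the weeks 20-24 set everywhere else; the two imiquimod arms also have different missed-dose rules

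*Combined protocol and SAP*

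**What the plan says.** **Timing of the outcome**

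- Section 1.1 (both primary objectives): "histologic regression to CIN 1 or less at weeks 20-24 (4 to 8 weeks after the end of imiquimod treatment"). Section 1.2.1 gives the same weeks for complete regression.
- Section 5.1: the primary outcome is read from "cervical biopsies collected during weeks 20-24 (4-8 weeks after completion of Imiquimod therapy").
- Sections 6.2.2 and 9.1: the final visit is week 22, window weeks 20-24. Every woman has colposcopy and biopsy there for the primary endpoint. In the imiquimod arms the visit must fall a minimum of three weeks after the final dose.
- Section 6.2.2 also says: "Persistence of CIN 2-3 or worsening cervical dysplasia diagnosed at the 20-24 weeks visit will be recommended for treatment with surgical conization".
- Section 10.11, regression: "Histologic regression of all index lesions to CIN 1 or less at 12 to 16 weeks after end of imiquimod treatment period". Remission: "Complete regression of cervical dysplasia at all index biopsy sites at 12 to 16 weeks after end of imiquimod treatment period". The opening sentence of 10.1 gives the same 12-16 weeks.
- Section 15.5 places the outcome "after completion of the 12 to 16 weeks imiquimod course" and says that the definition and "how it is determined is described in Section 5.1". Section 15.6 repeats the course wording for remission and HPV clearance.

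**Dosing rules**

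- Section 6.2.1, imiquimod only: a missed dose may be made up the next day; failing that, it is skipped.
- Section 6.2.1, imiquimod plus vaccine: next-day make-up is allowed and the dosing period may also be lengthened so that all doses are taken. No limit is given.
- Section 7.3: "At the end of the 16-week period, any remaining medication will be collected".

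**The concern.** Section 10 is where the plan defines its response criteria, and its time does not match the time at which the outcome is measured. Only 10.11 says how a woman is classified: all index lesions must be at CIN 1 or less, new high-grade lesions count as persistence, and worsening counts as progression. Section 5.1 covers collection, central review and blinding, but not these categories. The analyst therefore needs 10.11 for the classification and has to disregard its time. Section 15.5 adds a further wording by describing a 16-week course as lasting 12 to 16 weeks. The same pair of numbers is thus an interval after treatment in Section 10 and a course length in Section 15.

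The dosing rules matter for a different reason. The two imiquimod arms should differ only in the vaccine. As written, one of them can receive imiquimod for longer and be biopsied later, with no matching delay in the other arm or in controls. The modified ITT set in Section 15.2 has no window condition and does not say what makes a measurement valid, so a late biopsy could count.

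**Working it through.** **1. The window in Sections 1.1 and 5.1.** Section 6.2.1 gives a 16-week course. Then 20 - 16 = 4 and 24 - 16 = 8, so weeks 20-24 are 4-8 weeks after imiquimod. The plan's own figures agree with each other and with the week 22 ± 2 visit in 9.1.

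**2. The window in Sections 10.1 and 10.11.** 16 + 12 = 28 and 16 + 16 = 32, so weeks 28-32. This is a shift of 8 weeks (28 - 20, 32 - 24), with 28 - 24 = 4 weeks between the windows. Using the lower end of the 15.5 course wording does not rescue it: 12 + 12 = 24 and 12 + 16 = 28, which touches the visit window only at week 24.

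**3. Could Section 10.11 be met on schedule?** Section 9.1 lists no study biopsy after week 22 ± 2. The later 3- and 6-month follow-up in 6.2.2 is a Pap smear and high-risk HPV test. Women with CIN 2-3 at weeks 20-24 are recommended for conization, which would remove the lesion before week 28. It could not be met.

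**4. Which window governs?** Section 15 opens by applying its methods to the objectives in 1.1 to 1.3. Objectives 1.1.1, 1.1.2 and 1.2.1 all say weeks 20-24. Section 15.5 sends the reader to 5.1, which says weeks 20-24. Nothing in Section 15 refers to Section 10.

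**5. Limit on extended dosing.** A biopsy by week 24 and at least 3 weeks after the last dose implies a last dose by 24 - 3 = week 21, an extension of at most 21 - 16 = 5 weeks. The plan does not state this limit. Section 5.2 loosens it for HPV testing by offering the three-week gap as an alternative to weeks 20-24.

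Where the last dose would fall if all doses were taken:

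- One 21-day pause (Section 7.1.1): 16 + 3 = week 19.
- Menses suspensions alone, assuming 28-day cycles and no next-day make-up: about 4.5 doses missed, 4.5 / 3 = 1.5 weeks, so week 17.5.
- Both: week 20.5.
- Two full 21-day pauses: 16 + 6 = week 22, the only one of these cases beyond week 21.

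**6. Effect of late biopsies in the vaccine arm.** Assumptions: a constant spontaneous rate giving the planned 28% at week 22; the same rate in all women who have not yet regressed; delays of 3 to 5 weeks. The share delayed is not in the documents, so a range is shown.

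Gain in regression probability per delayed woman, for delay d in weeks:

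- No treatment effect: 0.72 × (1 - 0.72^(d/22)) = 3.15 points (d = 3) and 5.18 points (d = 5).
- At the planned 63%: 0.37 × (1 - 0.72^(d/22)) = 1.62 and 2.66 points.

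Shift in the difference from control, in points:

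| Share of arm delayed | No effect | Planned 63% |
|---|---|---|
| 10% | 0.32-0.52 | 0.16-0.27 |
| 20% | 0.63-1.04 | 0.32-0.53 |
| 40% | 1.26-2.07 | 0.65-1.06 |

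Standard error of the difference with 38 per arm: √(2 × 0.28 × 0.72 / 38) = 0.103 with no effect, and √((0.28 × 0.72 + 0.63 × 0.37) / 38) = 0.107 at 28% v 63%. That is about 10 points.

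**The case against.** The best defence is that Section 10 carries leftover text and the intent is not in doubt. The objectives, 5.1, the visit schedule and both pointers in Section 15 agree on weeks 20-24. No histology is planned at weeks 28-32, so there are no rival data from which to choose. All of this stands, and it limits the consequence to a mistimed definition.

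A reader might go further and infer that the endpoint time is open, so that an analyst could pick a window after seeing results, or that power would suffer from a later biopsy. The documents do not support this. It would require outcome biopsies that the plan does not schedule, and leaving in place lesions that it recommends for conization.

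On dosing, the defence is that the three-week gap in 6.2.2 names both imiquimod arms, so the imiquimod-only text was probably just not updated, and that the visit window already implies a limit. Both are plausible. A reader might also infer that the extension seriously biases the comparison with control; the figures above do not bear that out.

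What the defence does not remove is that Section 10 is current text in version 11.0, that it is the only home of the response categories, and that the two arms have different written rules.

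**Conclusion.** The time in 10.1 and 10.11 is wrong as written. It affects the definitions of the primary outcome and of the first secondary outcome, and no on-schedule biopsy can satisfy it. This rests only on the 16-week course and calendar arithmetic. Sample size, the primary test and the visit schedule are unaffected. It is a wording error that should be corrected before analysis.

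The unequal missed-dose rules and the clash with 7.3 are also real, but minor. The shift of about 1 point or less depends on the assumed 20% delayed and the constant-rate model. Even at 40% it is about 2 points at most, a fifth of the standard error. The reason to harmonise the rules is that the imiquimod arms should be treated alike, not that a material bias is expected.

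**What to change.** 1. In 10.1 and in both 10.11 definitions, replace the interval of 12 to 16 weeks after imiquimod with weeks 20-24.
2. In 15.5 and 15.6, replace "after completion of the 12 to 16 weeks imiquimod course" with weeks 20-24, and cite 10.11 together with 5.1 for the definition.
3. In 6.2.1, give both imiquimod arms one missed-dose and extension rule. If extension is kept, state that the last dose falls by week 21, pauses included, so that the biopsy can be at least 3 weeks later and no later than week 24. The 4-8 weeks in 1.1, 1.2.1 and 5.1 should then be described as counted from a 16-week course.
4. In 5.2, require weeks 20-24 in all arms and add the three-week gap for the imiquimod arms only. In 7.3, collect leftover drug when dosing ends.
5. Report time from randomisation to biopsy by arm.

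The cost is an amendment to wording and one descriptive table, with no added visits or patients. An earlier cap (week 19 or 20) would leave more room for scheduling, but it is a preference and the plan does not need it. With the week 21 limit, a woman with two full 21-day pauses would forgo about (22 - 21) × 3 = 3 suppositories; the other cases worked through above lose none.

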12.0 STUDY MONITORING AND REPORTING PROCEDURES

12.1 Personnel responsible for the safety review and its frequency:

The principal investigator will be responsible for monitoring the data, assuring protocol compliance, and conducting the safety reviews at the specified frequency which must be conducted at a minimum of every 6 months (including when re-approval of the protocol is sought). During the review process, the principal investigator will evaluate whether the study should continue unchanged, require modification/amendment, or close to enrollment. Either the principal investigator, the IRB or the Yale Cancer Center Data and Safety Monitoring Committee (DSMC) have the authority to stop or suspend the study or require modifications.

12.2 The risks associated with the current study are deemed moderate for the following reasons:

- 1. The risk of progression of CIN 2,3 to invasive cervical cancer over 6-8 months from time of initial diagnosis is low and observation of CIN 2 diagnosed in young women for up to 12 to 24 months is already recommended by the ASCCP.
- 2. The risks associated with the FDA-approved drugs imiquimod and 9-valent HPV vaccine are minimal.

Although we have assessed the proposed study as one of moderate risk, the potential exists for anticipated and/or unanticipated adverse events, serious or otherwise, to occur since it is not possible to predict with certainty the absolute risk in any given individual or in advance of first-hand experience with the proposed study methods. Therefore, we provide a plan for monitoring the data and safety of the proposed study as follows:

12.3 Attribution of Adverse Events:

Adverse events will be monitored for each subject participating in the study and attributed to the study procedures / design by the principal investigator [name], according to the following categories:

a.) Definite: Adverse event is clearly related to investigational procedures(s)/agent(s).

HIC#: 1603017415 Protocol version 11.0

CIN 2/3 26

- b.) Probable: Adverse event is likely related to investigational procedures(s)/agent(s).
- c.) Possible: Adverse event may be related to investigational procedures(s)/agent(s).
- d.) Unlikely: Adverse event is likely not to be related to the investigational procedures(s)/agent(s).
- e.) Unrelated: Adverse event is clearly not related to investigational procedures(s)/agent(s).

12.4 Plan for Grading Adverse Events:

The following scale will be used in grading the severity of adverse events noted during the study:

- 1. Mild adverse event
- 2. Moderate adverse event
- 3 Severe

12.5 Plan for Determining Seriousness of Adverse Events:

An adverse event may be graded as severe but still not meet the criteria for a Serious Adverse Event. Similarly, an adverse event may be graded as moderate but still meet the criteria for an SAE. It is important for the PI to consider the grade of the event as well as its "seriousness" when determining whether reporting to the IRB is necessary.

Refer to Section 13.0 of the protocol for guidelines

12.6 Plan for reporting Reportable Adverse Events and other unanticipated problems involving risks to subjects or others to the IRB

The principal investigator will report the following types of events to the IRB: a) adverse events that are serious or life-threatening AND unanticipated (or anticipated but occurring with a greater frequency than expected) AND possibly, probably or definitely related to the drug/device/intervention; and b) other unanticipated problems involving risks to subjects or others.

These adverse events or unanticipated problems involving risks to subjects or others will be reported to the IRB in accordance with IRB Policy 710, using the appropriate forms found on the website. **This information is discussed in Section 13.0 of the protocol.**

12.7 Plan for reporting adverse events to co-investigators on the study, as appropriate the protocol's research monitor(s), e.g., Yale Cancer Center Data and Safety Monitoring Committee (DSMC), Protocol Review Committee (PRC), DSMBs, study sponsors, funding and regulatory agencies, and regulatory and decision-making bodies.

For the current study, the following individuals, funding, and/or regulatory agencies will be notified (choose those that apply):

X All Co-Investigators listed on the protocol.

HIC#: 1603017415 Protocol version 11.0

X Yale Cancer Center Data and Safety Monitoring Committee (DSMC)

The principal investigator [name] will conduct a review of all adverse events upon completion of every study subject. The principal investigator will evaluate the frequency and severity of the adverse events and determine if modifications to the protocol or consent form are required.

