12.8 ADVERSE EVENT REPORTING

This study will utilize the CTC version 4.0 for toxicity and Adverse Event Reporting. A copy of the CTC version 4.0 can be downloaded from the CTEP home page.

Toxicity Grade	Type ^a	Local IRB	Study Coordinators Via email/fax/phone
4,5	Unknown	Yes	Yes
5	Known	No	Yes*
2,3	Unknown	No	No
4	Known	No	No

^{*} If clearly related to the commercial agent(s)

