12.10 PROCEDURES FOR ELICITING AND RECORDING ADVERSE EVENTS

12.10.1 Eliciting Adverse Events

A consistent methodology for eliciting AEs at all subject evaluation time points should be adopted. Examples of non-directive questions include:

"How have you felt since your last clinical visit?

"Have you had any new or changed health problems since you were last here?"

12.10.2 **Specific Instructions for Recording Adverse Events**

Investigators should use correct medical terminology/concepts when reporting AEs or SAEs. Avoid colloquialisms and abbreviations. All information will be recording using Oncore Clinical Trials Management System.

HIC#: 1603017415 Protocol version 11.0

CIN 2/3

30

a. Diagnosis vs. Signs and Symptoms

If known at the time of reporting, a diagnosis should be reported rather than individual signs and

symptoms (e.g., record only liver failure or hepatitis rather than jaundice, asterixis, and elevated

transaminases). However, if a constellation of signs and/or symptoms cannot be medically

characterized as a single diagnosis or syndrome at the time of reporting, it is ok to report the

information that is currently available. If a diagnosis is subsequently established, it should be

reported as follow-up information.

b. Deaths

All deaths that occur during the conduct of the research must be reported to the Yale Principal

Investigator and the Remote Monitoring Coordinator immediately (if possible) to ensure that all

over site committees are properly informed. All information will be entered into Oncore Clinical

Trials Management System and updated appropriately. Further determination regarding the need

to submit to the subjects local IRB, Yale University HHRP following IRB Policy 710 for reporting

Unanticipated Problems Involving Risk to Subjects will be reviewed. Specific information is

outlined in section 13.0 of the protocol.

When recording a death, the event or condition that caused or contributed to the fatal outcome

should be reported as the single medical concept. If the cause of death is unknown and cannot be

ascertained at the time of reporting, report "Unexplained Death".

c. Preexisting Medical Conditions

A preexisting medical condition is one that is present at the start of the study. Such conditions

should be reported as medical and surgical history.

A preexisting medical condition should be re-assessed throughout the trial and reported as an AE

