13.1 Expedited Reporting of UPISROs Occurring at Yale

AEs classified as "serious" and "unexpected" that are possibly, probably, or definitely attributed to drug administration, or SAEs whose frequency exceeds expectations, require expeditious handling and reporting.

Serious Adverse Event (SAE)

Any adverse event that results in any of the following outcomes:

- death.
- a life-threatening experience,
- inpatient hospitalization or prolongation of existing hospitalization,
- a persistent or significant disability/incapacity,
- a congenital anomaly/birth defect, or
- any other adverse event that, based upon appropriate medical judgment, may jeopardize the subject's health and may require medical or surgical intervention to prevent one of the other outcomes listed in this definition.

The PI will promptly investigate all safety information related to an adverse experience. If the results of the PI's investigation show an adverse drug experience not initially determined to be reportable (based on whether the event is serious, unexpected, and associated with drug administration) is so reportable, the PI will report such experience. Follow-up information to a safety report shall be submitted as soon as the relevant information is available.

Reporting to the Yale Human Investigation Committee

Timeframe for Reporting

- 1. Events that may require a temporary or permanent interruption of study activities by the Principal Investigator or sponsor to avoid potential harm to subjects should be reported to the IRB **immediately** (if possible), followed by a written report to the IRB using the UPIRSO Reporting Form (710 FR 4) **no more than 5 calendar days** after the Yale Principal Investigator becomes aware of the event.
- 2. Internal Events (defined above) should be reported to the IRB using the UPIRSO Reporting Form (710 FR 4) within 5 calendar days of the Principal Investigator becoming aware of the event.
- 3. External Events (defined above) should be reported to the IRB using the UPIRSO Reporting Form (710 FR 4) **within 15 calendar days** of the Yale University Principal Investigator (PI) becoming aware of the event ONLY IF either of the following are true:
 - (a) The Yale PI has concluded that an immediate change to the protocol is necessary to address the risks raised by the event, and BI agreed to the changes OR

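### The 12.8 table marks unknown Grade 2-3 events as not reportable, which contradicts the seriousness-based rules in 12.5, 12.6 and 13.1 when such an event is serious and related

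*Combined protocol and SAP*

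**What the plan says.** Several parts of Sections 12 and 13 bear on what is reported and to whom.

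- **12.4** introduces a severity scale with the words "The following scale will be used in grading the severity of adverse events noted during the study" and lists three levels: mild, moderate, severe.
- **12.5** says that severity and seriousness are different things, and that "an adverse event may be graded as moderate but still meet the criteria for an SAE".
- **12.6** sends an event to the IRB if it is serious or life-threatening, unanticipated (or anticipated but more frequent than expected), and at least possibly related. It sets no grade threshold.
- **12.8** states "This study will utilize the CTC version 4.0 for toxicity and Adverse Event Reporting". Its table then routes events by grade and by known or unknown type. The row for unknown Grades 2 and 3 reads "2,3 Unknown No No", the last two columns being the local IRB and the study coordinators.
- **12.10.2b** says "All deaths that occur during the conduct of the research must be reported", naming the principal investigator and the Remote Monitoring Coordinator as recipients. Whether the IRB must also be told is left to further review.
- **13.1** requires expedited handling of serious, unexpected, at least possibly attributed events, "or SAEs whose frequency exceeds expectations, require expeditious handling and reporting". It too sets no grade threshold.

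**The concern.** The protocol contains two reporting rules built on different variables. One turns on seriousness, expectedness and relatedness; the other on grade and known or unknown type. They need not give the same answer, and for unknown Grade 2-3 events the table gives an explicit No rather than silence. A coordinator working from the table, which is the quickest reference in the section, could properly conclude that a report is not needed when 13.1 requires one within 5 calendar days for an internal event. At stake is the timeliness of safety information reaching the IRB, not the efficacy analysis.

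**Working it through.** No arithmetic applies; the check is to set each row of the 12.8 table against 12.6 and 13.1.

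| 12.8 row | Local IRB | Coordinators | Under 12.6 and 13.1 | Result |
|---|---|---|---|---|
| 4, 5 unknown | Yes | Yes | Reportable if serious and at least possibly related | Table is broader: it has no relatedness condition |
| 5 known | No | Yes, if clearly related to the agent | Reportable if more frequent than expected, or if unexpected and related | Conflict in limited cases |
| 2, 3 unknown | No | No | Reportable if serious and at least possibly related | Direct conflict |
| 4 known | No | No | As for 5 known, if serious | Conflict in limited cases |

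**The direct conflict, worked through one case.** Take a reaction not listed for either product, judged possibly related, CTC Grade 3, leading to an unplanned admission.

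1. 12.10.2d makes an adverse event that results in hospitalization an SAE, and the SAE definition in 13.1 includes inpatient hospitalization.
2. Being unlisted, it is unexpected under 12.9.5. If the literature does not describe it either, it is unknown under 12.8.
3. Being possibly related, it meets all the conditions of 12.6 and of the first limb of 13.1.
4. The trial is single-site (14.1), so the event is internal, and 13.1 allows 5 calendar days to report it.
5. The 12.8 table returns No for the IRB and No for the coordinators.

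The protocol itself expects that Grade 3 events can be serious. Table 8 lists hospitalization among the supportive measures for Grade 3 anaphylaxis, and Table 3 describes Grade 3 respiratory events needing intravenous or operative intervention. Those reactions may be known ones; they show only that Grade 3 and serious can coincide.

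**The known Grade 4 and 5 rows.** An anticipated serious event occurring at its expected frequency is not IRB-reportable under 12.6 or 13.1, so No is consistent with those sections. The rows fail in two situations. The first is excess frequency, which 12.6 and 13.1 both cover. The second is an event that 12.8 calls known and 12.9.5 calls unexpected. The footnote to 12.8 sets type by whether the toxicity appears in the package insert or literature and does not mention severity. 12.9.5 counts a listed toxicity as unexpected when its specificity or severity goes beyond the package insert or brochure.

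**Deaths.** The table tells coordinators of a known Grade 5 event only if it is clearly related. 12.10.2b covers all deaths without that condition. The named recipients are not described in the same terms, so the two passages need reconciling.

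**Grading scale.** 12.4 stops at severe. CTC v4.0, with Grades 4 and 5, is adopted in 12.8 and used in 6.2.1, in the Section 7 tables and in 10.13. The mismatch is between 12.4 and those sections. It does not touch 12.5, 12.6 or 13.1, because those turn on seriousness.

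**The case against.** The strongest reply is that a missed report would require someone to read one table in isolation. 12.10.2d already makes a hospitalized event an SAE; 12.5, 12.6 and 12.9.2 point to Section 13; 12.9.3 makes the investigator responsible for reporting as set out in 12.10 and 13.0; and 12.6 gives IRB reporting to the principal investigator under its own criteria. Under 12.7 the co-investigators and the DSMC are notified, and the principal investigator reviews all adverse events as each subject completes.

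This stands as a limit on the consequence: the documents do not show that such events would go unreported, or that oversight would necessarily hear late. It does not remove the contradiction. 12.8 is headed as the adverse event reporting section, includes Grades 4 and 5 (so it is not confined to minor toxicity), has no SAE exception and does not refer to Section 13. 12.9.3 adds a further formulation, under which all AEs and SAEs go to the appropriate IRB(s), without ranking the rules.

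Three stronger readings are tempting and are not supported:

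- *That the table wrongly keeps known deaths from the IRB.* As a general statement this fails. 12.6 and 13.1 do not require IRB reporting of an anticipated event at its expected frequency, and 12.10.2b does not send every death to the IRB.
- *That Grades 4 and 5 cannot be assigned because 12.4 has only three levels.* CTC v4.0 is adopted in several other places, and Grade 4 and 5 rows appear in the management tables. 12.4 is one inconsistent list.
- *That the three-level scale contradicts the seriousness rules.* 12.5 separates severity from seriousness, so it does not.

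**Conclusion.** The 12.8 table is wrong as written for unknown Grade 2-3 events that are serious and at least possibly related: it says No twice where 12.6 and 13.1 say report. Of its four rows, one conflicts outright in that situation, two (known Grade 4, known Grade 5) conflict only for excess frequency or for events unexpected under 12.9.5, and one is broader than 12.6. The 12.4 scale is a secondary wording mismatch with CTC v4.0.

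The number of events affected cannot be stated, because the documents give no expected count. The conclusion assumes that the table is meant to apply to SAEs as well as other events; nothing in 12.8 says otherwise. It does not assume that staff would follow the table over Section 13, only that the protocol does not tell them which to follow. The correction should be made, but it does not affect the trial's efficacy conclusions.

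**What to change.** Keep the 12.8 table and add one sentence beneath it: any SAE is assessed and reported under 12.6 and 13.1 regardless of its grade or table row, with unexpected defined as in 12.9.5. That sentence resolves both the direct conflict and the limited conflicts in the known Grade 4 and 5 rows. Reconcile the clearly-related condition for telling coordinators of a known death with 12.10.2b. Replace the three levels in 12.4 with the CTCAE v4 Grades 1-5 already used elsewhere.

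An override is better than deleting the table in favour of the 12.6 and 13.1 criteria. Deletion would lose its Yes for unknown Grade 4-5 events, which carries no relatedness condition, and its coordinator-notification column. The cost is a wording amendment and possibly a few more IRB reports; no treatment, visit or analysis changes.
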